#### xii. Study limitations and the expected results

##### *Study Limitations*

This is an exploratory study with a small sample size that is not adequately powered for statistical comparisons of the EED outcomes (non-invasive biomarkers). As a result, the findings of this study may not be widely generalizable. This limitation will be mitigated during presentation of the study findings, which will avoid drawing conclusions beyond the scope of the study methods. The expected results from the study are intended to be useful for establishing a safety profile and reasonable pediatric dose and providing study design considerations (e.g., child EED biomarker data) for future research on the efficacy of AA-ORS and the deployment of similar EED interventions in LRS.

#### xiii. Itemized budget and budget justification

##### *Budget*

Category	Amount (USD)
PERSONNEL	[redacted]

TRAVEL	[redacted]
EQUIPMENT & SUPPLIES	[redacted]
WORKSHOPS & TRAINING	[redacted]
PARTICIPANT SUPPORT COSTS	[redacted]
OTHER PROJECT COSTS	[redacted]
Overhead	[redacted]
Total	[redacted]

#### *Budget justification*

The largest budget item for this study is personnel costs, totaling USD [redacted], which includes salaries and benefits for the study PIs and co-investigators as well as the research assistants, clinical staff, and lab personnel required to implement a quality study. Travel costs of USD [redacted] include international travel for non-Kenyan investigators to attend study trainings and site visits as well as domestic transportation for study staff to travel to the study site. Equipment and supply expenses include paper and printing costs for study materials, biomarker assays, and acylcarnitine mass-spectrometry, totaling USD [redacted]. Workshops and trainings are budgeted to cost USD [redacted] and include the initial training of all study staff on the protocol and consenting process to be followed for this study. A total of USD [redacted] is budgeted for participant support costs to pay individuals according to the compensation scheme outlined in the informed consent document. Other project costs of USD [redacted] include fees for ethical and regulatory submissions, shipment and procurement of study product and placebo, legal and contracting support, among other miscellaneous expenses.

#### xiv. Research study data collection forms and other references

*Appendix 1 – Informed Consent Form*

*Appendix 2 – Case Report Forms (CRF)*

*Appendix 3 – Patient Information Leaflet*

*Appendix 4 – Investigator’s Brochure*

*Appendix 5 – Recruitment Scripts for Caregivers*

*Appendix 6 – Patient Instruction Sheet*

*Appendix 7 – Letter of Support From [name]*

*Appendix 8 – Toxicity Table*

### i. Risks to research study participants/groups

#### *Risk Considerations*

The proposed study is expected to be of minimal risk as the study AA-ORS is a medical food product regulated by the US FDA. As a result, we do not anticipate any adverse events for this study related to the administration of AA-ORS, but we will include a control arm in order to better assess the safety of this product in children with mild-moderate stunting. Children with mild to moderate stunting are at increased risk for morbidity and mortality, so we anticipate that participants may report diarrhea or respiratory infections at high rates, regardless of receipt of active AA-ORS or placebo. While there is mounting evidence that microbiome immaturity contributes to growth deficits in LRS, any changes to the microbiome composition and diversity from provision of AA-ORS are likely to be transient, based upon previous observations among infants and children provided probiotic-supplemented formula or ready-to-use supplementary food (43, 44).

This study involves blood specimen collection. The collection of these samples involves venipuncture, which may cause discomfort, pain, introduction of infection, bleeding, fainting, or bruising. Precautions will be taken to avoid introduction of infection by disinfecting the site of venipuncture and using sterile equipment. The risk of bleeding and bruising will be minimized by immediate application of pressure after venipuncture. The child will be restrained appropriately by the caregiver to prevent kicking of the phlebotomist. A thorough description of potential risk considerations and mitigation strategies is outlined in Table 7.

**Table 7.** Known risks and mitigation strategies for SAFE study participants.

Potential risk to participant	Concern	Study design feature intended to minimize risk	Rationale for the necessity of exposing participants to risk
Reduction in breastmilk consumption among those breastfeeding at enrollment.	Consumption of solution (AA-ORS or placebo) could reduce amount of breastmilk consumed by child.	Exclusion of exclusively breastfed children.  Caregivers instructed to provide breastmilk as needed during the 3-hour dosing period.  Monitoring for decreased frequency of breastfeeding and for unplanned (by caregiver) weaning. Will stop the study if it is clear there is a major reduction in breastfeeding from the study drink.	Ingestion required for product delivery.  Overall caloric content of AA-ORS unlikely to satiate children given daily intake requirements.
Use in pediatric populations who are acutely ill.	Children experiencing mild-moderate stunting are at increased risk for morbidity and mortality and may develop intercurrent illnesses during the course of the study.	Will recruit children with mild to moderate stunting (length-for-age z-score between -1 and -3), but not acute illness at enrollment.  Safety monitoring procedures in place to identify and treat adverse events.	Children with stunting, with or without acute illness, overlap considerably with the target population for an EED intervention.
No safety data in children.	Prior safety data on the study AA-ORS is from adult populations and may not apply to pediatric subjects.	Will directly observe the first dose of the product in the clinic to identify any acute reaction.  Will treat all participants who experience adverse events during follow-up.	Study is needed to establish the safety profile of the product.  May also assess whether children's metabolism switches to oxidation.
Spoilage/contamination.	Open AA-ORS bottles could pose a health risk if consumed at a later time, due to contamination.	Mark and reseal bottles using tape and markers provided at enrollment. Research assistant (RA) to visit home on second and fourth day of follow-up to instruct and advise caregiver on safe storage and proper resealing of bottles after maximum of 3 hours.	Need to measure and calculate the average daily volume consumed during follow-up in order to guide dosing recommendations in future clinical trial.

Potential risk to participant	Concern	Study design feature intended to minimize risk	Rationale for the necessity of exposing participants to risk
		RAs to pick up partial and empty bottles 1–2 times per week.	
Volume of solution too great.	237 ml may be too much volume for children.	Children to drink as much or as little of the solution (up to 237 ml) as desired over 3 hours. Gavage will not be done. Breastmilk will be permitted throughout this period.	Need to measure and calculate the average daily volume consumed during follow-up in order to guide dosing recommendations in future clinical trial.
Blood draw in children.	Potential discomfort, bleeding, bruising, and minimal risk of infection.	Precautions will be taken to avoid introduction of infection by disinfecting the site of venipuncture and using sterile equipment. The risk of bleeding and bruising will be minimized by immediate application of pressure after venipuncture.  Only trained, experienced phlebotomist will perform venipunctures.	Blood samples are needed in order to measure metabolic profile and biomarkers of gut dysfunction, systemic inflammation, and micronutrient status.  Metabolic profile assessment will be an important part of exploratory analysis; it is helpful to determine if the absence of certain essential amino acids leads to increase in oxidative pathways.  These biomarker measurements are important in order to have setting-specific descriptive data with which to power a future EED efficacy trial.  A comparison of these non-invasive biomarkers following the intervention will also be done.
Loss of confidentiality.	Medical information from a participant's medical record or other	Access to study records will be limited to study staff with electronic passwords (data files) or	Review of medical records will help ensure that only eligible

Potential risk to participant	Concern	Study design feature intended to minimize risk	Rationale for the necessity of exposing participants to risk
	study documents are shared inappropriately.	lock and key (physical records).  Study staff will only review medical records for eligibility assessment and will not make copies or remove such records from the hospital premises.  If the caregiver declines enrollment in the study, any medical record data collected will be discarded.	participants are enrolled in the study.  Detailed study records are critical for data analysis and reporting results accurately.

The information participants will provide in the context of this study is not considered sensitive and will not pose any significant risk to them personally. There is a minimal risk of loss of confidentiality. All study staff will be trained in the protection of human subjects, including maintaining participant confidentiality. Study procedures will begin only after the appropriate ethics committees grant approval.

As the sponsor of this study, PATH will secure clinical trials insurance, which will cover the costs associated with any study-related injuries.

#### *Benefits*

No direct benefit is anticipated to participants for their inclusion and participation in this study. Information collected during this study may benefit the participants' community in the future for potential EED interventions administered in an aqueous solution, including but not limited to the study AA-ORS.

#### *Rights of the Study Participants*

Provisions will be made to protect the participants in this study. Confidentiality, anonymity, and storage of data and specimens will be explained to all participants or their caregivers (i.e., parent or legally acceptable representative). The participants will be informed that they may withdraw from this study at any time with no negative repercussions for themselves or the child participant. All data collection tools and biological samples will be identified only with the individual study participant number and study title. It will be made clear that only the study team will have access to the data that emerges from this study and the data will be only used for research purposes.

#### *ii. Access to protected health information required by proposed research study*

The study will have access to protected health information. The use of patient medical records will be necessary to help ensure that only eligible participants are enrolled in the study (e.g., confirm the child does not have chronic health conditions such as HIV, hepatitis B, or hepatitis C).

### iii. Sources of data, specimens, and records to be used in the proposed research study

#### *Data Collection Procedures*

Data collection tools (e.g., IDI guides and questionnaires) will be administered by study staff in the language of the caregiver's preference. Participants will be allowed to ask questions in order to obtain clarification on study procedures.

#### Clinical information

Adverse events will be assessed via clinician-directed physical examination (screening, enrollment visit, and day 15 visit) and signs and symptoms reported by participants (days 1, 4, 7, and 14). Data collected at interim visits will use a structured questionnaire to record interval medical history. All clinical information collected as part of this study will be stored on password-protected computers in PATH offices.

#### IDs:

Interviews will be conducted by an RA trained in qualitative methods. During the IDs, the interviewer will guide the flow of the discussion. Any other member of the IDI team present will take note of topics that generate more animated discussions, participants' attitude, body language, and interactions among the interviewer and interviewee. Notes will be documented in an unstructured format and saved as part of the participant study record. Discussions will be guided by a semi-structured data collection guide (Appendix 2), with responses hand-written contemporaneously by the interviewer.

The interview guides will be a mix of structured and semi-structured questions. Structured questions will be necessary for standardizing responses to particular questions. Semi-structured questions will allow for flexibility and richness in responses, especially those on perceptions of facilitators and barriers for AA-ORS uptake. Semi-structured questions are open-ended and will allow for probing a participant's answers for in-depth responses.

Post-dosing IDs with caregivers will be conducted after use of study product with their child in a private setting (Appendix 2). Caregiver interviews will last between 45 to 60 minutes at enrollment and post-dosing visits.

#### DO of product administration:

DO will be conducted with caregivers and their child during the very first study product administration at the enrollment visit. AA-ORS or placebo solution will be provided to participants by study staff. The DO will last up to three hours, depending on how quickly the child drinks the product. The researcher will take notes contemporaneously during the DO.

#### Blood samples:

All samples collected as part of this study will be stored in freezers at Kakamega CGH. Samples may be shipped to Kilifi and/or Nairobi for analysis at laboratories operated by Kenya Medical Research Institute (KEMRI).

### iv. Maintaining confidentiality of research study data and protecting the participant privacy

All participants will be assigned unique identification numbers in place of their names to maintain confidentiality. All data will be stored on password-protected computers in PATH offices. Only members of the study team will have access to the raw transcripts and consent forms in a locked filing cabinet.

#### v. Storage of data and specimens being collected

All data will be stored on password-protected computers in PATH offices in Kenya and the United States. All plasma/serum specimens will be labeled with alphanumeric patient and sample identification numbers and stored in a freezer at Kakamega CGH until shipment. Specimens will be prepared for shipment on dry ice in compliance with recognized standards for air transport and will be transported to KEMRI labs in Nairobi and/or Kilifi, Kenya by a third-party shipper with experience with biological specimens. Once the samples have arrived at the KEMRI laboratory, they will be unloaded into a freezer (temperature  $\leq 20^{\circ}$  C), before being assessed using the immunoassays described in Table 5. Dried bloodspots will be shipped to KEMRI or another third-party laboratory in Kenya with the necessary mass spectrometry equipment to run metabolomic analyses. All plasma/serum specimens collected will analyzed for the study, and remaining specimens will be destroyed within 5 years. We have included language in the consent form to allow for potential future research with the samples and data related to nutrition or infectious diseases.

#### vi. Duration of data storage, ensuring data security, and custodian and staff with data access

A permanent master set of data will be kept by PATH at least 5 years post-completion of the funded project, but may be stored indefinitely. All data will be stored on password-protected computers in PATH offices. Only members of the study team will have access to the raw transcripts and consent forms in a locked filing cabinet. De-identified patient data will be shared with the manufacturer of the product.

#### vii. Plan for controlling access to stored research study data

All data will be stored on password-protected computers in PATH offices. De-identified patient data will be shared in an electronic format with the manufacturers of the AA-ORS. Explicit permission from PATH is required before the manufacturers can license the de-identified study data to a third party.

#### viii. Viewing of identifiable research study data by persons unlisted as applicant or study team member

Research assistants, study nurse, and study pediatrician will be contracted to conduct the IDIs and other study procedures as outlined above. These individuals shall collect and or view research study data with identifiers during enrollment and data collection activities in order to carry out visits and project activities. The RAs will not have access to the identifiable data once it has been entered into an electronic format and data cleaning and analysis is complete.

#### ix. Signing of agreement(s) by research study team members with access to confidential data collected

All study staff will have signed agreements protecting confidentiality of research data prior to conducting any study activities.

#### x. Potential benefits of research study to community and/or society

##### *Benefits*

No direct benefit is anticipated to participants for their inclusion and participation in this study. Information collected during this study may benefit the participants' community in the future for potential EED interventions.

## xi. Consent issues: how consent will be obtained

### *Consent Process*

Informed consent is the process of ensuring that potential participants fully understand what will and may happen to them while participating in a research study. An information sheet describing the study product (Appendix 3) will be provided to participants before the consent process begins. All consent materials, including any non-English translations, will be approved by the PATH REC and MUERC prior to use.

In the region where this study is conducted, Luhya is the predominant ethnic group. However, there is no single Luhya language and there are over 10 different Luhya dialects spoken and mutually understood. Kiswahili is commonly spoken and understood as well, so documents translated into the local language will be translated into Kiswahili. Study staff will be conversant in local dialects in addition to Kiswahili to help ensure adequate comprehension of the consent materials.

All study staff will be trained and certified in the protection of human subjects. In obtaining and documenting informed consent, the study staff will comply with applicable local and domestic regulatory requirements and will adhere to GCP and to the ethical principles that have their origin in the Declaration of Helsinki.

Before an individual is enrolled in this study, it is the site investigators' responsibility to ensure that informed consent is obtained from the participant after adequate explanation of the aims, methods, and potential risks and benefits of the study. The consent form will be reviewed and discussed with potential participants in a private space where others cannot easily overhear the conversation. The informed consent process will give individuals all the relevant information they need to decide whether to participate in this study. Potential research participants will be permitted to ask questions and to exchange information freely with the study team prior to providing written consent. We will not restrict enrollment to literate individuals, as we intend to recruit patients with caregivers from a variety of education levels. However, the requirement for caregivers to own a cellphone is closely associated with basic literacy. In the case of an illiterate potential participant, an independent witness must be present for the entire consenting process and will have to sign and date the informed consent form. In addition, the illiterate participant will also put a thumbprint on the consent form. Consent will be documented by having the participant sign and date the appropriate consent form. The study staff obtaining consent will also sign and date the consent form. A signed and dated copy of the consent form will be given to the participant.

### *Cost/Volunteer Benefits*

There is no financial cost to the participants in this study. Caregivers in this study will receive a nominal compensation for their time and involvement. Compensation values and distribution mechanism will be documented in the informed consent form, and the value for the enrollment/consent visit will be greater than that of the day 15 visit based upon the longer duration of the initial visit. PATH will provide appropriate treatment or reimbursement for the treatment of injuries directly attributable to participation in this study.

## F. APPENDIX 8 – TOXICITY TABLE

Solicited symptoms grading scale

Parameter	Grade 1 Mild	Grade 2 Moderate	Grade 3 Severe	Grade 4 Potentially Life-Threatening
CLINICAL				
Clinical adverse event NOT identified elsewhere in the grading table	Mild symptoms causing no or minimal interference with usual social & functional activities with intervention not indicated	Moderate symptoms causing greater than minimal interference with usual social & functional activities with intervention indicated	Severe symptoms causing inability to perform usual social & functional activities with intervention or hospitalization indicated	Potentially life-threatening symptoms causing inability to perform basic self-care functions with intervention indicated to prevent permanent impairment, persistent disability, or death
Dermatologic				
Pruritus [Itching] (without skin lesions)	Itching causing no or minimal interference with usual social & functional activities	Itching causing greater than minimal interference with usual social & functional activities	Itching causing inability to perform usual social & functional activities	NA
Rash	Localized rash	Diffuse rash OR Target lesions	Diffuse rash AND Vesicles or limited number of bullae or superficial ulcerations of mucous membrane limited to one site	Extensive or generalized bullous lesions OR Ulceration of mucous membrane involving two or more distinct mucosal sites OR Stevens-Johnson syndrome OR Toxic epidermal necrolysis

 Adapted from the Division of AIDS Table for Grading the Severity of Adult and Pediatric Adverse Events, version 2.1, March 2017, of the United States National Institutes of Health. This table is available at <https://rsc.tech-res.com/clinical-research-sites/safety-reporting/daids-grading-tables>.

Parameter	Grade 1 Mild	Grade 2 Moderate	Grade 3 Severe	Grade 4 Potentially Life-Threatening
Gastrointestinal				
Bloating or Distension	Symptoms causing no or minimal interference with usual social & functional activities	Symptoms causing greater than minimal interference with usual social & functional activities	Symptoms causing inability to perform usual social & functional activities	NA
Constipation	NA	Persistent constipation requiring regular use of dietary modifications, laxatives, or enemas	Obstipation with manual evacuation indicated	Life-threatening consequences (e.g., obstruction)
Diarrhea < 1 year of age	Liquid stools (more unformed than usual) but usual number of stools	Liquid stools with increased number of stools OR Mild dehydration	Liquid stools with moderate dehydration	Life-threatening consequences (e.g., liquid stools resulting in severe dehydration, hypotensive shock)
Vomiting	Transient or intermittent AND No or minimal interference with oral intake	Frequent episodes with no or mild dehydration	Persistent vomiting resulting in orthostatic hypotension OR Aggressive rehydration indicated (e.g., IV fluids)	Life-threatening consequences (e.g., hypotensive shock)
Neurologic				
Seizures < 18 years of age (includes new or pre-existing febrile seizures)	Seizure lasting < 5 minutes with < 24 hours postictal state	Seizure lasting 5 to < 20 minutes with < 24 hours postictal state	Seizure lasting ≥ 20 minutes OR > 24 hours postictal state	Prolonged and repetitive seizures (e.g., status epilepticus) OR Difficult to control (e.g., refractory epilepsy)
Systemic				

Parameter	Grade 1 Mild	Grade 2 Moderate	Grade 3 Severe	Grade 4 Potentially Life-Threatening
Acute Allergic Reaction	Localized urticarial (wheals) with no medical intervention indicated	Localized urticarial with intervention indicated OR Mild angioedema with no intervention indicated	Generalized urticarial OR Angioedema with intervention indicated OR Symptoms of mild bronchospasm	Acute anaphylaxis OR Life-threatening bronchospasm OR Laryngeal edema
Lethargy	Symptoms causing no or minimal interference with usual social & functional activities	Symptoms causing greater than minimal interference with usual social & functional activities	Symptoms causing inability to perform usual social & functional activities	Incapacitating symptom of lethargy causing inability to perform basic self-care functions
Fever	38.0 °C to < 38.6 °C	≥ 38.6 °C to < 39.3 °C	≥ 39.3 °C to < 40.0 °C	≥ 40.0 °C
Weight Loss	NA	5% to < 9% loss in body weight from baseline	≥ 9% to < 20% loss in body weight from baseline	≥ 20% loss in body weight from baseline OR Aggressive intervention indicated (e.g., tube feeding, total parenteral nutrition)

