#### v. Number and age range of research study participants/groups whose data shall be used

Sixty-six children between the ages of 12 and 24 months and their caregivers will be enrolled into the study.

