#### vi. Inclusion criteria for each group of research study participants

##### *Inclusion Criteria*

##### Pediatric and caregiver pairs (must meet inclusion criteria for both categories):

###### Child:

1. Is between 12 and 24 months of age.
2. LAZ between  $-1$  and  $-3$  SD.
3. At least one week post routine immunization or vitamin A supplementation visit at the study site.
4. Has a parent or legally acceptable representative willing and able to provide informed consent.
5. No plans for travel outside of the community for the duration of the study.

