#### *Definition of Adverse Event (AE)*

An adverse event (AE) is any untoward medical occurrence in a participant after administration of the study product and that does not necessarily have a causal relationship with the study product. An AE can therefore be any unfavorable and unintended signs (including abnormal laboratory findings), symptoms, physical examinations, or disease temporally associated with the use of the study product, whether related to the study product or not. This definition includes exacerbations of pre-existing conditions. Stable pre-existing conditions that do not change in nature or severity during the study are not considered AEs; however, these should be reported as part of the medical history.

**Solicited AEs** are pre-specified adverse events that are actively monitored by study staff during the full 21 days of follow-up. Personal communication with the study product manufacturer indicated that no adverse events have been found to be associated with the AA-ORS in adult studies or in the small study (n=5) featuring children with short bowel syndrome.

For this study, solicited AEs will be assessed by study nurse 30 minutes after the first administration (in person), and then by phone on days 4, 7, 14, and 21.

The following specific solicited adverse events will be monitored for this trial:

- *Vomiting.*
- *Diarrhea.*
- *Fever.*
- *Constipation.*
- *Lethargy.*
- *Irritability/restlessness.*
- *Allergic reactions:* sudden swelling of the face or throat, itching, and rash.
- *Other reactions:* fits (convulsions/seizures); gas, abdominal cramps, or stomach pain; weight loss.

Changes in the severity of an AE (e.g., diarrhea) will be documented to allow an assessment of the duration of the event at each level of severity to be performed. AEs characterized as intermittent require documentation of onset and duration of each episode.

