#### *Severity of Adverse Events*

The severity of all AEs will be assessed by the study clinician based on the following guidelines.

- **Mild**—Events require minimal or no treatment and do not interfere with the participant's daily activities.

- **Moderate**—Events result in a low level of inconvenience or concern. Moderate events may cause some interference with functioning and may require therapeutic measures.
- **Severe**—Events that prevent a participant’s usual daily activity and require systemic drug therapy or other treatment. Of note, the term “severe” does not necessarily equate to “serious.”
- **Potentially Life-Threatening**—Events that require emergency room visit or hospitalization. Potentially life-threatening symptoms causing incapacitation with intervention needed to prevent disability or death.

A toxicity table for solicited AEs with guides for assessing severity of the specific event is found in Appendix 8.

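### The only diarrhea row in the Appendix 8 toxicity table is for children under 1 year, so the event-specific severity guide covers none of the 66 participants aged 12–24 months

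*Combined protocol and SAP*

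**What the plan says.** Eligibility is fixed by age. Child inclusion criterion 1 reads "Is between 12 and 24 months of age", and section C.v repeats it for the whole sample: "Sixty-six children between the ages of 12 and 24 months and their caregivers will be enrolled into the study".

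Severity is addressed in two places:

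- **Severity of Adverse Events (section C.x)** opens with "The severity of all AEs will be assessed by the study clinician based on the following guidelines" and gives four levels, from mild to potentially life-threatening, with no age restriction. It closes with "A toxicity table for solicited AEs with guides for assessing severity of the specific event is found in Appendix 8".
- **Appendix 8** grades on four levels with the same names. Its single diarrhea row is labelled for children under 1 year of age. Grade 1 is "Liquid stools (more unformed than usual) but usual number of stools". Grade 2 is liquid stools that are more numerous, or mild dehydration. Grades 3 and 4 are defined by moderate dehydration and by life-threatening consequences. A catch-all row at the top of the table takes clinical events that are not "identified elsewhere in the grading table".

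Diarrhea is a listed solicited event, and it is the protocol's own example of an event whose severity is followed over time: "Changes in the severity of an AE (e.g., diarrhea) will be documented to allow an assessment" of how long it lasts at each level (Definition of Adverse Event).

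**The concern.** A grading row that excludes every eligible child leaves the clinician without an applicable event-specific guide for a solicited event. Risk Considerations (section D.i) expects diarrhea to be reported at high rates in either arm, so the gap would be met often.

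At stake is the consistency of recorded severity. The study clinician assigns it, and under Study Monitoring the independent study monitor confirms it for all adverse events. If each works from a different scale, both can follow the protocol and still disagree. Because the two scales share the same four level names, a recorded Moderate would not show which scale produced it. The severity description would then be harder to interpret in the safety profile that the study is meant to pass on to later research (Study Limitations).

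**Working it through.** No sample size, power or error rate is involved. The check sets the sections side by side.

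**1. Does the row cover any participant?** The row applies to ages below 12 months, and eligible ages are 12 to 24 months. The two ranges do not overlap, so the number covered is 0 of 66.

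**2. Could the label be a loose pediatric tag?** The seizure row in the same table is labelled for those under 18 years, which does include these children. Age labels in this table therefore carry meaning, and the diarrhea label is narrower than the study population.

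**3. Does the catch-all row take over?** It is reserved for events not listed elsewhere in the table. Irritability is a solicited event without a row of its own, so it passes to the catch-all cleanly. Diarrhea does have a row, so on a literal reading the catch-all does not apply, even though that row excludes the child.

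**4. Does the general guideline take over?** It is stated for all adverse events and has no age limit, so a grade can always be assigned.

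**5. Do the scales agree?** Take a child with liquid stools, more of them than usual, no dehydration, no interference with activity and no intervention indicated.

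| Scale | Deciding feature | Grade |
|---|---|---|
| General guideline, Severity of Adverse Events | little or no treatment, no interference with activity | Mild |
| Appendix 8 catch-all row, if used | no or minimal interference, intervention not indicated | Grade 1 (Mild) |
| Appendix 8 diarrhea row, as printed | liquid stools with a higher count | Grade 2 (Moderate) |

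The same episode differs by one level. The result depends on the conditions stated: if an intervention is indicated, the catch-all row no longer gives Grade 1. This example shows a conflict at the Mild/Moderate boundary only; none is shown at Grades 3 or 4.

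**6. What uses the grade?**

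- Duration at each severity level (Definition of Adverse Event): yes.
- The independent monitor's confirmation of severity (Study Monitoring): yes.
- Fisher's exact test on adverse events and serious adverse events (Data Analysis Procedures): not as written.
- Chi-square test on diarrhea classes of 1–2, 3–4, 5–7 and 7+ events in 24 hours: no, it uses counts.
- Stopping rules: no, they use weight loss and cessation of breastfeeding.
- Definition of a serious adverse event: no, it does not refer to the table.

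**The case against.** The strongest reply is that nothing breaks. The general guideline covers all adverse events at any age, and the protocol calls Appendix 8 a set of guides. A clinician can grade every diarrhea episode without the infant row. Staff are blinded and both arms use the same forms, so inconsistent grading gives no evident advantage to either arm. No test or stopping rule depends on the result. On this view the age label is a slip in an appendix.

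Most of that stands, and it limits the point. It does not remove it. The protocol explicitly directs solicited events to Appendix 8, that table and the guideline can disagree on a plausible episode, and no sentence ranks one over the other.

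Three stronger readings are tempting, and the documents do not support them:

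- **A reader might infer that diarrhea severity cannot be graded.** The general guideline shows that it can. The defect is an inapplicable event-specific row and unclear precedence.
- **A reader might infer that the stool-count classes in the analysis plan contradict the grading row.** They serve a different part of the endpoint, changes in digestive habits, and a severity grade need not share their cut-points.
- **A reader might treat diarrhea as the main gut-related safety event.** The protocol lists it beside vomiting, constipation and abdominal symptoms without ranking them.

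**Conclusion.** The point holds as an inconsistency in a working safety instrument. The diarrhea row that the protocol relies on for event-specific grading covers 0 of 66 children. The available fallback can differ from the printed row by one level, Mild against Moderate, for episodes with raised stool frequency, no interference with activity and minimal or no treatment.

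The consequence is limited to diarrhea severity reporting and to the monitor's severity check. A reader might go further and infer that the primary safety comparison is compromised or biased between arms. The documents do not support that, because neither planned test uses the grade and grading is blinded. How often the two scales would diverge cannot be estimated, since the documents give no expected distribution of diarrhea episodes by type. The correction is worth making because it is nearly free.

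One assumption matters: that the appendix text available is complete. The table runs over several pages, and a second diarrhea row for older children could have been lost when it was converted to text. No gap is marked and the neighbouring rows follow in order, but the sponsor can settle this by looking at the source file.

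**What to change.** 1. Check the Appendix 8 diarrhea row against the grading table cited in its footnote, and replace it with a row that covers children aged 12–24 months. The source's criteria for this age are not reproduced in the protocol, so the sponsor must take them from the source. No grading criterion is proposed here.
2. Add one sentence under Severity of Adverse Events saying either that Appendix 8 governs solicited events or which scale prevails when the two differ.
3. If the final row depends on the child's usual number of stools, confirm that the existing enrollment and stool-frequency forms record it. A stool-frequency questionnaire is already part of the nurse check-ins, so a new item is needed only if the forms lack this.

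The cost is one table row and one sentence. Sample size, visits, procedures and planned tests are unchanged.
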